### ***WIC Program Variables***

A key variable of interest in assessing infant feeding practices is the mother's experience with the WIC program. There is variation in participants' experiences with WIC because there are differences in: (1) the services and education provided at the local clinic, (2) the State policies and supplies provided (3) the training and attitudes of the local WIC clinic staff, and (4) the time spent in the program. Westat proposes to improve the measure of participants' WIC program experience and capture this variation by developing a series of composite measures. We propose five composite

measures for capturing program variation and identify the expected contributing factors to each measure as follows:

- **Variation in education offered** measured by the number of education contacts offered, educational topics offered, delivery method, training of the staff, knowledge and attitudes of the staff. (In addition to this program-offering composite, we will have information on the educational programs the individual attended which can be used as a separate covariate).
- **Variation in breastfeeding peer counseling** measured by the ratio of counselors to participants, education and training of the staff, and knowledge and attitudes of the staff; and
- **Variation in the provision and support for breast pumps** measured by types of pumps available, policies on issuance, support education provided, and knowledge and attitudes of the staff regarding pumps
- **Variation in the food packages** measured by package choice substitutions available based on the State plan and attitudes of the staff regarding the importance of the food packages, substitutes, and alternative diets.
- **Variation in time in WIC** measured by number of days of current participation, number of years of participation associated with previous children, joined pre-natal or post-partum.

We will use these composite variables to capture the cross-sectional variation in WIC program experience, or “dosage” of WIC exposure, among program participants.

It should be noted that ultimately the variation in service delivery we observe between sites will determine which factors to include in our composite measures as well as whether the final measures are effective in capturing meaningful program variation that can be related to policies. Therefore, to some extent this work will be exploratory and we will assess alternative composites. For example, if we find the quality of sites’ educational programs vary by phase we will consider having separate composites for newborn feeding, infant feeding transition, and toddler feeding. In contrast, if sites that deliver effective newborn feeding education, almost always also deliver strong infant feeding transition and toddler feeding programs, a single education composite will suffice.

---

The WIC program variables will be composite measures. A composite measure is a combined metric that incorporates multiple individual measures to provide a single score. It is used as a way to measure concepts that are too complex to be measured simply with one item. Composite measures are also a data reduction technique used to avoid having many highly correlated variables in the same analyses which creates statistical challenges. The five WIC program variables will be composite measures of the component variables listed in the Research Plan and are intended to capture different aspects of how the program is being delivered and experienced. For each of the five composite measures, we will develop weights for the component variables and combine them into a single score (index variable). A simple approach for doing this is to take a straight average of all the component variables but this approach would not address the differing importance of the component items or their correlation with each other. We propose to use factor analysis (a statistical technique) to determine the relative weights to use in the creating the composite measure.

As we discuss in the study sampling plan, we will develop a typology and collect information from the States regarding WIC program features that will be used to stratify sites for sampling. Once the sample of service sites is selected, we will collect more detailed information from these sites regarding their WIC program features and operations through a series of key informant interviews. Together, these data will capture both State and local policies and offerings and will allow us to develop more refined categorical measures of the WIC program that reflect the variation in supplies, services, and educational offerings among service sites. Finally, through the staff survey, we will collect information on staff training and attitudes.

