**Table 7-3. Proposed model specifications**

Model	Dependent variable	Estimation methods	Minimum covariates to explore
Breastfeeding decision	
 
■ Initiating breastfeeding
 
■ Breastfeeding at hospital discharge
 
 Measured dichotomously and categorically (all breastfeeding, combination, all formula)	
 
■ Logistic regression (dichotomous)
 
■ Multinomial logistic regression (categorical)
 
	
 
■ Socio-demographics: Age, race/ethnicity, born in US, father in house, infant first born, income, poverty level, education, worked during pregnancy
 
■ Maternal and infant health: Mother's post-delivery health status, infants health status (measured as in NICU or more than 6 weeks premature or very low birth weight)
 
■ Prenatal attitudes, beliefs and knowledge: Perceived benefits of breastfeeding, perceived barriers, breastfeeding intentions
 
■ Prenatal experience and advice: breastfed previous children, receipt of advice to breastfeed from physician, receipt of advice to breastfeed from family, receipt of breastfeeding information from non-WIC sources
 
■ WIC program experience: Education, peer counseling, time in WIC
 
■ Hospital experience: Mom's length of stay, baby's length of stay, receipt of formula or bottle in gift package, had baby friendly practices
 

Table 7-3. Proposed model specifications (continued)

Model	Dependent variable	Estimation methods	Minimum covariates to explore

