Formula Supplementation	
 
■ Time until formula supplementation
 
	
 
■ Survival analysis
 
	
 
■ Socio-demographics: Age, race/ethnicity, born in US, infant first born, use of childcare, education, worked during pregnancy
 
■ Maternal and infant health: Mother's post-delivery health status, infants health status, birth weight, reported problems breastfeeding
 
■ Prenatal attitudes, beliefs and knowledge: Perceived benefits of breastfeeding, perceived barriers, how long intend to breastfeed
 
■ Prenatal experience and advice: Receipt of advice to breastfeed from physician, receipt of breastfeeding information from non-WIC sources
 
■ WIC program experience: Education, peer counseling, breast pumps, time in WIC
 

Breastfeeding cessation	
 
■ Time until cessation
 
	
 
■ Survival analysis
 
	
 
■ Socio-demographics: Age, race/ethnicity, born in US, infant first born, education, use of child care
 
■ Maternal health: Reported breastfeeding problems
 
■ Breastfeeding practices: Current use of formula
 
■ Prenatal attitudes, beliefs and knowledge: Perceived benefits of breastfeeding, perceived barriers, how long intend to breastfeed
 
■ Prenatal experience and advice: Receipt of advice to breastfeed from physician, receipt of breastfeeding information from non-WIC sources
 
■ WIC program experience: Education, peer counseling, breast pumps, time in WIC
 
■ Return to work/school: Returned to work/school within 2 months
 

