Finally, in all these models we will capture the cross-sectional variation in the WIC program experience through the inclusion of WIC program composite measures which will be an enhancement over past studies. For breastfeeding initiation and duration decisions, we expect that the variation in educational programs, peer counseling and the provision and support for breast pumps will be factors affecting individuals' decision. For infant feeding transitions and toddler weight outcomes, we expect that variation in education and the food packages will be important factors. For all of these decisions and outcomes, we expect that the time the mother has spent in WIC will be an important predictor.

This page left intentionally blank

Table 8-1 provides a summary of our proposed analytical report schedule and the content of each report. There are a few topic areas that draw solely from data collected during the first few interviews and these analyses can be completed prior to finishing all the data collection. Analyses of prenatal views, the study design and sample, breastfeeding decisions, hospital practices and neonatal circumstances, and breastfeeding problems can be completed prior to conducting the 13 months interview. Additionally, the analyses on formula supplementation, breastfeeding and formula feeding practice, and the continuation and cessation of breastfeeding can be completed using data through the month 13 interview. The analyses of all the other topic areas at least partially depend on data collected from later interviews. Therefore, as our report schedule shows, there are some topics for which we will provide preliminary analysis based on the currently available data and then update these analyses in final infant and final infant and toddler reports. Please note, that while we are contracted to deliver 4 interim reports on the toddler interviews, since FNS eliminated the 21 month interview, we have only 3 data collection interviews. We have some suggestions for the content of the 4th report we would like to discuss with FNS.

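### The time-in-WIC dosage score counts days of current participation with no end date; in the survival models a count that runs to the event would build the outcome into the exposure

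*Combined protocol and SAP*

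**What the plan says.** Section 7.2 (WIC Program Variables) defines variation in time in WIC as "measured by number of days of current participation, number of years of participation associated with previous children, joined pre-natal or post-partum". It gives no start or end date for the first item, "number of days of current participation". On use, the section says: "We will use these composite variables to capture the cross-sectional variation in WIC program experience", which it describes as dosage of WIC exposure. Footnote 17 makes each composite a single index and adds: "We propose to use factor analysis (a statistical technique) to determine the relative weights".

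Table 7-3 then places time in WIC in every model:

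- Breastfeeding decision model (initiation, breastfeeding at discharge): "WIC program experience: Education, peer counseling, time in WIC".
- Formula supplementation and breastfeeding cessation, both survival analyses: "Education, peer counseling, breast pumps, time in WIC". In the cessation model these items are in italics, which Section 7.5 uses for additions to be explored.
- Introduction of other foods (survival analysis), weight, and growth: time in WIC is listed with education and, for weight and growth, food package.

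Of all these decisions and outcomes, the close of Section 7.5 says: "we expect that the time the mother has spent in WIC will be an important predictor".

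Section 2.1 says the conceptual models help to identify lagged influences, but no lag, landmark or time-varying form is given for time in WIC. Table 3-2 shows that the child's age when WIC was discontinued is asked at every interview from month 1 to month 24.

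**The concern.** Days of participation keep accruing while the outcome is still pending. A fixed score cannot include post-birth days in a time-to-event model without using either the event time or what happened after it.

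The recruitment rules sharpen this. Under Section 4.2, women enter the study as they enrol in WIC for this pregnancy or infant, so the day count is about zero at study entry and can vary only through later accrual. For women who join after the birth, every counted day falls after delivery, and so after the usual moment of initiation.

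Section 7.3 presents these models as causal. An artefact here would look like the result the study hopes to see: more WIC going with longer breastfeeding and later formula. Stopping the count at the outcome date can look like good practice, so an analyst could choose it in good faith.

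**Working it through.** The documents state no effect size or numeric result for this covariate, so there is no figure to reproduce. The check is of the mechanism.

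**Definition.** Let A be days in WIC before birth, T the child's age at the event, W the child's age at WIC exit, and E the age at which counting stops. For a prenatal joiner the dose is D = A + min(W, E). For a postnatal joiner who enrols at child age e, D = max(0, min(W, E) − e).

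**Stopping at the event.** Set E = T with the mother still in WIC: D = A + T. Take two mothers who each enrolled 100 days before birth, one weaning at 30 days and one at 180. Their doses are 100 + 30 = 130 and 100 + 180 = 280 days. Nothing about WIC differs between them; the gap of 150 days is the outcome.

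**Null simulation.** Breastfeeding duration was generated independently of WIC time, and a Cox model was fitted with dose as a fixed covariate per 30.4 days.

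- From the documents: 20 percent leaving WIC (Section 4.9 gives this for the 3-year collection period; the simulation applied it over 24 months).
- Assumed: exponential breastfeeding duration with median 30 to 180 days; prenatal WIC time uniform over 1 to 240 days; 20% postnatal joiners; follow-up of 395 days.
- Size: 3 replicates of 1,200 mothers per setting.

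Hazard ratio of cessation per month of dose when the true value is 1:

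| Median duration (days) | Count to birth | Count to cessation | Count to interview reporting it | Count to WIC exit or 24 months |
|---|---|---|---|---|
| 30 | 0.995 | 0.864 | 0.858 | 0.995 |
| 60 | 1.006 | 0.823 | 0.826 | 1.003 |
| 120 | 0.994 | 0.802 | 0.814 | 0.993 |
| 180 | 1.012 | 0.804 | 0.819 | 1.008 |

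The correlation of dose with breastfeeding duration is about 0 (−0.02 to 0.02) for the count to birth and 0.45 to 0.79 for the count to cessation. With 10% or 40% postnatal joiners and a median of 60 days, the count to cessation gives 0.81 and 0.82.

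**Other assumptions.** A second set used 20,000 simulated mothers, 40% weaned by 2 months and prenatal time uniform over 0 to 7 months. It gives 0.74 to 0.75 for the count to the event and 1.00 for pre-birth days only. The spread from about 0.75 to 0.86 comes from these assumptions, none of which the documents settle.

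**Counting past the event.** If WIC exit depends on weaning, the long count picks up some reverse causation. With 30% (assumed) leaving WIC when they wean, it gives 0.99 and a correlation of 0.09. With exit 1.5 to 3 times likelier after weaning (assumed), it gives 0.98 to 0.99.

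**Inside a composite.** In null runs that placed the event-stopped count in a three-item score, the hazard ratio was 0.63 to 0.71 per standard deviation of the score. The weights had to be assumed, so this shows only that the artefact survives combination.

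**Initiation and discharge.** There is no event time in a logistic model. The issue there is order: any day counted after birth (initiation) or after discharge comes after the outcome it is meant to predict.

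**The case against.** The strongest reply is that the plan never says the count runs to the event. A reader might infer that, as written, the analysis is bound to show a protective WIC effect, or that longer breastfeeding necessarily raises the dose. The documents do not support either reading: the cut-off is simply absent, and a count to birth, or to WIC exit or 24 months, shows little or no distortion. That limit is accepted.

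A reader might also extend the artefact to every model listing time in WIC. It does not reach weight at 6, 12 and 24 months, where the outcome age is fixed and contains no event time. Nor should the 0.75 to 0.86 range be read as the bias in the planned coefficient. It applies to raw days as the only covariate, whereas the plan enters days with two other items under weights not yet known.

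The plan also leaves room to do this well. Section 2.1 mentions lagged influences, the cessation model includes current formula use, which suggests changing covariates may be in mind, and Section 7.2 says of the composites: "to some extent this work will be exploratory and we will assess alternative composites". But that last flexibility concerns which service features vary between sites, not the timing of a person-level count. Section 7.5 also allows alternative proxies to be tried when a first choice is not significant, so a correctly timed null count could be replaced by one that is significant only through the artefact.

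Finally, freezing the count at birth discards postnatal exposure, and a time-varying status can itself reflect leaving WIC after weaning. Both points stand and shape the fix.

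**Conclusion.** The point holds in conditional form. An accruing day count enters the survival models as a fixed score without a stated cut-off. If counting stops at the event or at the interview reporting it, a null effect appears as a hazard ratio of roughly 0.75 to 0.86 per month of raw days, a spurious reduction of 14% to 25%. If counting runs to WIC exit or 24 months, the ratio is 0.98 to 1.01, but the score draws on information from after the event. Stopping at birth gives 0.99 to 1.01. In the initiation and discharge model, later days are post-outcome exposure.

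The hazard ratios rest on assumed breastfeeding durations, prenatal WIC time and share of postnatal joiners; they show direction and order of magnitude. The bias in the final composite cannot be computed from the documents. This is more than a missing detail, because no fixed score that includes post-birth days avoids both problems in a time-to-event model.

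**What to change.** State the counting window for each model in Section 7.2 or Table 7-3.

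- **Initiation and discharge:** count only days enrolled before delivery, alongside years with previous children and prenatal or postpartum entry.
- **Formula supplementation, cessation, introduction of foods:** use the same pre-birth measure. If postnatal exposure is wanted, add cumulative WIC days or in/out status as a lagged time-dependent covariate, or use a count to a landmark age among those still at risk. The lag is there to limit reverse causation from mothers who leave WIC after weaning.
- **Weight at fixed ages:** stop the count at or before the age of measurement.

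The cost is a redefinition of one composite and slightly more analysis work. No new data are needed, since enrolment timing is known and age at WIC discontinuation is collected at each postnatal interview (Table 3-2). The drawback is that pre-birth days are zero for all postnatal joiners, whose later exposure is then carried only by the time-dependent or landmark term.

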### 7.3 Main Types of Analyses

We will conduct both descriptive and causal analyses to answer the 60 research questions and update the analyses from past studies of the WIC program. Many of the research questions can be answered by descriptive analyses that tabulate the responses to specific questions (e.g., what are the mother's reported breastfeeding problems?) or characterize the attributes and behaviors of different subpopulations (e.g., what are the distributions of caregiver and participants health-related characteristics by race and ethnicity of the mother?). A small subset of the research questions focus on understanding the underlying population and program factors that drive nutritional outcomes and decisions. Therefore, we will conduct basically four types of analyses as follows:

- **Descriptive analyses**
  - Single month cross-sectional snap shots
  - Repeated monthly (or key month) cross-sectional snap shots
  - Longitudinal calculations (i.e. we read across several interview months to calculate the measure of interest such as the average age children start cereal)
- **Causal analyses**
  - Model estimations

We will use descriptive statistics (counts, proportions, means, medians, distributions (percentiles), means, medians,) and cross-tabulations) to examine key decisions and conditional outcomes by subgroups (e.g., how do the feeding practices of infants and children who continue in WIC compare

to those who leave the program^18 or have non-continuous participation?). For questions like these, the differences will be examined between subgroups by comparing descriptive statistics across subgroups such as the proportions that engage in given feeding practices. This will determine if the subgroup statistics are different using the appropriate statistical significance tests (e.g., Chi test for proportions and t-test for means that are adjusted for the cluster sample design). The advantage of descriptive cross tabulations is they are straightforward but they will not capture the impact multiple factors may be having on a decision or outcome and therefore may overstate the importance of the subgroup variables.

For the subset of the research questions that focus on identifying the causal relationships that drive the outcomes and decisions observed, we will use multivariate analyses such as regression analysis to explore how choices and characteristics impact feeding practice decisions and nutrition outcomes while holding other contributing factors constant. We will use Ordinary Least Squares (OLS) regression, logistic and multinomial logistic regression, survival analysis, quantile regression, and growth models to answer these questions. We will apply OLS regression models to explore how continuous dependent variables are, on average, impacted by background characteristics, experiences, and decisions. We will use Logistic (and multinomial) regression to model how dichotomous (and categorical) decisions and outcomes (e.g., the decision to breastfeed) are impacted by background characteristics, experiences, and past decisions. Similarly, we will use survival analyses to model how background characteristics, experiences, and past decisions affect time duration until an event (e.g., number of day until breastfeeding cessation). Finally, for investigating weight outcomes, we will initially explore the relationships between predictors and outcome using OLS regression but then will use quantile regression to estimate impact that the explanatory variables have on the dependent variable quantiles (we propose using quintiles but will also explore other slices of the distribution). This will provide insight into how the explanatory variables affect each weight/length quintile (top 20 percent of the distribution, etc.) rather than the mean level as OLS regression does. Additionally, we will use growth models to estimate the impact that covariates have on the weigh/length growth trajectory.

---

We will continue to interview women who leave the WIC program with the understanding that there may be a drop off in their interview cooperation rate.

## 7.4 Data Challenges

Over a two year data collection period, it is highly likely that participants will miss some of the interviews. First, we will minimize the number of missing variables by repeating questions across interviews and recording the date of change of critical behaviors. For example, if a woman stops breastfeeding in month 5 and misses the month 5 interview, we will capture when she stopped in the 7-month interview. Second, as we discuss in our sampling plan, we use a combination of imputation for key variables and weight to address issues of missing data.

In addition to missing specific interviews, we are likely to have some individuals for which the data are censored (all their data are missing either prior to or after a specific date). This is likely to occur for several reasons including (1) individuals drop out of the study, (2) the study timeline is not long enough to observe the variable of interest for all participants, and (3) mothers enter the study at different times during their pregnancy or postpartum. Left censoring will be an issue for women who join WIC after their babies are born and we will address these cases by separately examining relevant subsamples based on time period they entered the study. In cases of right censoring, as long as the censoring is independent—unrelated to the subsequent risk of the event— within a covariate group (e.g. women who return to work), the hazard function (the failure rate in survival analyses) can be estimated. For example, right hand censoring may occur because women drop out of the study and we do not observe a key outcome such as the when they stopped breastfeeding. In these cases, we will only know that they breastfed up to a point in time. As long as there are no unobservable factors that systematically affect who leave the study, we can still include the censored data in estimating the hazard function without bias.

